## **7.7 EXTENT OF EXPOSURE**

Exposure will be presented as categorized period of [REDACTED]

[REDACTED] based on dose received for total study medication intake. Only descriptive statistics are planned for this section of the report. Summaries will be provided on FAS during treatment period. Total exposure (in days) is defined as date of last administration of study medication - date of first administration of study medication+ 1, ignoring the temporary interruptions, i.e. intermittent off-treatment periods were considered in the extent of exposure.

## **7.8 SAFETY ANALYSIS**

All safety analyses will be performed on the FAS during on-treatment period.

### **7.8.1 Adverse events**

Analyses of adverse events will be descriptive in nature. All analyses of AEs will be based on the number of patients with AEs and NOT on the number of AEs.

The analysis of AEs will be based on the concept of treatment emergent AEs. That means that all AEs occurring between first drug intake till - after last drug intake will be assigned to the randomised treatment. All AEs occurring before first drug intake will be assigned to 'screening' and all AEs occurring after last drug intake - will be assigned to 'follow-up' (for listings only). For details on the treatment definition, see Section 6.1.

According to ICH E3 (10), in addition to Deaths and Serious Adverse Events, 'other significant' AEs need to be listed in the clinical trial report. These will be any non-serious adverse event that led to an action taken with study drug (e.g. discontinuation or dose reduced or interrupted).

For further details on summarization of AE data, please refer to the guideline 'Handling and summarization of adverse event data for clinical trial reports and integrated summaries' ill:

An overall summary of adverse events will be presented.

The frequency of subjects with AEs will be summarised by treatment, primary system organ class and PT (mention MedDRA levels to be displayed in the tables). Separate tables will be provided for subjects with SAEs, AEs leading to treatment discontinuation, AEs of at least moderate severity and related AEs with significant non-serious adverse events

The system organ classes will be sorted by default alphabetically, PTs will be sorted by frequency (within SOC). Customized sorting orders may also be used based on trial needs, e.g. SOC sorted by frequency.

The following are considered as protocol-specified AESI:

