| Comparator product(s) | Placebo to BI 764198 |
| dose | Not applicable |
| mode of administration | Oral (p.o.) or, only if needed, nasogastric intubation |
| Duration of treatment | Up to 28 days |
| Statistical methods | 
The primary endpoint will be analysed with a logistic regression model using covariates of treatment, severity grade at baseline, age, creatinine at baseline, and duration of symptoms before hospitalisation, to evaluate the absolute difference in proportions of patients alive and free of mechanical ventilation at Day 29 with BI 764198 and placebo. Patients who terminate the study medication prematurely will be followed and the events which occur after premature discontinuation of medication and before the time point of interest will be included in the analysis using the Full Analysis Set (FAS).
 
The logistic regression for the primary endpoint analysis will be used for other binary endpoint(s) and time-to-event endpoints will be analysed using Cox regression including covariates used for the primary analysis. Ventilator free days will be analysed using ANCOVA including the same covariates as in the primary analysis.
 |

FLOW CHART

| Trial Periods | Screening | Treatment | | | Follow-up (telephone visits only ^b) | | |
|--|----------------------|---------------|---------------------------|---|--|-----------------------|-----------------------------|
| | | 1 | 2 | 3 through 29 | EOT ^a | FUP ^b 1 | FUP ^b 2, 3, 4 |
| Visit | | | | | | | |
| Day | -1 | 1 | | Daily Day 2 through discharge -1 day (maximum Day 28) | discharge/ day after last dose | EOT +4 days | 15, 29, 60 (from Day 1) |
| Time window for visits (days) | -3 to 1 ^c | | | | | +2 | ±3 |
| Informed Consent | X | | | | | | |
| Demographics | X | | | | | | |
| Medical History | X | | | | | | |
| Baseline Conditions | X | | | | | | |
| Clinical Frailty Scale (CFS) | X | | | | | | |
| SARS-CoV-2 PCR test ^{c,h} | X | | | | | | |
| Review of inclusion/exclusion criteria ^c | X | X | | | | | |
| Randomisation | | X | | | | | |
| Concomitant Therapy and Procedures | X | X | X | X | X | X | X |
| Adverse event evaluation | X | X | X | X | X | X | X |
| Hospitalisation Status | X | X | X | X | X | X | X |
| World Health Organization (WHO) Clinical Progression Scale | X | X | X | X | X ^f | X ^f | |
| Ventilation and oxygen parameters; respiratory rate, FiO ₂ , SpO ₂ | X | X | X | X | X ^f | X ^f | |
| Vital signs (refer to Section 5.2.2) | X | X | X | X | | | |

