5.2.6.2 Adverse event collection and reporting

5.2.6.2.1 AE Collection

The investigator shall maintain and keep detailed records of all AEs in the patient files. The following must be collected and documented on the appropriate CRF(s) by the investigator:

- From signing the informed consent onwards until the follow-up Visit 1: all AEs (non-serious and serious) and all AESIs.
- After follow-up Visit 1 until the individual patient's end of trial: cancers of new histology and exacerbations of existing cancers, all trial treatment related SAEs and all trial treatment related AESIs.
- After the individual patient's end of trial:
the investigator does not need to actively monitor the patient for new AEs but should only report any occurrence of cancer and trial treatment related SAEs and trial treatment related AESIs of which the investigator may become aware of by any means of communication, e.g. phone call. Those AEs should be reported on the BI SAE form (see [Section 5.2.6.2.2](#)), but not on the CRF.

Vital Status Data Collection

Patients who discontinue trial medication prematurely, who agree to be contacted further, but do not agree to physical visits, should be followed up as described in [Section 3.3.4.1](#), withdrawal from trial treatment. From then on until the individual patient's end of the trial the investigator must report all deaths/fatal AEs regardless of relationship, and trial treatment related SAEs and trial treatment related AESIs the investigator becomes aware of.

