6.2.2 Treatment period(s)

The treatment period starts with Visit 2 (Day 1, randomization) and ends with the EOT visit (possible Day 2 through Day 29). Patients will remain hospitalised during the treatment period and daily protocol visits will be conducted to complete procedures according the [Flow Chart](#). Patients may receive treatment with study drug for up to 28 days, however if a patient is well enough to be discharged, then study drug may be stopped before the maximum treatment duration (i.e. 28 days).

EOT visit should be completed the day after the last dose of study drug is administered for all patients regardless of discharge status. EOT visit is expected to align with day of discharge, unless it is planned for a patient to remain hospitalised after treatment with study drug is stopped. EOT visit should occur no later than Day 29.

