7.2.5 Safety analyses

Adverse events will be coded using the Medical Dictionary for Drug Regulatory Activities (MedDRA). Standard BI summary tables and listings will be produced.

[REDACTED]

Proprietary confidential information © 2021 Boehringer Ingelheim International GmbH or one or more of its affiliated companies

All treated patients will be included in the safety analysis. In general, safety analyses will be descriptive in nature and will be based on BI standards. No hypothesis testing is planned.

Statistical analysis and reporting of adverse events will concentrate on treatment-emergent adverse events, i.e. all adverse events occurring between start of treatment and end of the REP. Adverse events that start before first drug intake and deteriorate under treatment will also be considered as 'treatment-emergent'.

Frequency, severity, and causal relationship of adverse events will be tabulated by system organ class and preferred term after coding according to the current version of the Medical Dictionary for Drug Regulatory Activities (MedDRA) at database lock.

Laboratory data will be analysed both quantitatively as well as qualitatively. The latter will be done via comparison of laboratory data to their reference ranges. Values outside the reference range as well as values defined as clinically relevant will be summarised. Treatment groups will be compared descriptively with regard to distribution parameters as well as with regard to frequency and percentage of patients with abnormal values or clinically relevant abnormal values.

Vital signs, physical examinations, or other safety-relevant data observed at screening, baseline, during the course of the trial and at the end-of-trial evaluation will be assessed with regard to possible changes compared to findings before start of treatment.

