## 7. PLANNED ANALYSIS

Descriptive statistics for continuous variables will be N (number of patients with non-missing values), mean, standard deviation (SD), minimum, median, and maximum. In general, means, SDs, will be presented to one more decimal place than the raw data. Minimums and maximums will be presented to the same number of decimal places as the raw data.

Tabulations of frequencies for categorical data will include all possible categories and will display the number of observations in a category as well as the percentage(%) relative to the respective treatment group. Percentages will be rounded to one decimal place. The category "missing" will be displayed only if there are actually missing values. Percentages will be based on all patients in the respective patient set no matter whether they have non-missing values or not.

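### Time at risk for adverse events depends on outcome, and the visible SAP specifies only percentages of patients, with no common-window or exposure-adjusted summary

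*SAP*

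**What the plan says.** **Length of treatment.** Drug is given in hospital for up to 28 days and may stop sooner if the patient is well enough to leave (Protocol 6.2.2). The EOT visit is the day after the last dose, whether or not the patient has been discharged, but "EOT visit is expected to align with day of discharge".

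**Collection.** Protocol 5.2.6.2.1 sets the full-collection window: "From signing the informed consent onwards until the follow-up Visit 1: all AEs (non-serious and serious) and all AESIs". FUP 1 is 4 days after EOT (Protocol 6.2.3). From then to the end of the trial at Day 90, only cancers and treatment-related SAEs and AESIs are collected.

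**Analysis window.** SAP 7.8: "All safety analyses will be performed on the FAS during on-treatment period". Protocol 7.2.5 defines treatment-emergent events as "all adverse events occurring between start of treatment and end of the REP". The length of that residual effect period is not visible in the public text. SAP 7.8.1 sends later events to follow-up, for listings only.

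**Summary measure.** SAP 7.8.1: "All analyses of AEs will be based on the number of patients with AEs and NOT on the number of AEs" and "The frequency of subjects with AEs will be summarised by treatment, primary system organ class and PT". On denominators, SAP 7 says: "Percentages will be based on all patients in the respective patient set no matter whether they have non-missing values or not". For further detail SAP 7.8.1 refers to a sponsor guideline on summarising adverse events. Exposure in days is tabulated (SAP 7.7) but is not linked to adverse events.

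**Fixed-day outcomes.** Mortality is analysed at Days 15, 29, 60 and 90, and the composite of in-hospital death, ICU admission or mechanical ventilation at Day 29 (SAP 7.5.2).

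**The concern.** Safety is part of the main objective (Protocol 2.1.1), and the drug is meant to change how fast patients recover. Time to response, which counts discharge, is a secondary endpoint, so the plan itself allows for stays that differ by arm. If they do, the period in which an adverse event can be counted differs too, and a percentage of all patients in the set takes no account of that. Two arms with the same daily risk can then show different percentages, and a real excess can be reduced.

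The same feature affects patients who stop drug early for any reason. With a last dose on Day 3, EOT is Day 4 and FUP 1 is Day 8. If that patient stays in hospital for weeks, a non-fatal SAE judged unrelated falls outside required collection after Day 8, although efficacy follows the same patient to Day 29 under treatment policy. With a last dose on Day 28, FUP 1 is Day 33. The summary of extrapulmonary organ failure (SAP 7.8.5) is built from reported adverse events and has the same limitation.

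**Working it through.** The plan states no adverse-event rate or expected stay, so there is no figure of its own to reproduce. What follows is an illustration on assumed inputs.

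**From the documents:** treatment of at most 28 days; EOT 1 day after the last dose; FUP 1 at EOT + 4, so full collection ends 1 + 4 = 5 days after the last dose; 65 patients per arm.

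**Assumed:** constant hazard *h* of a first event, equal in both arms (0.01, 0.03 or 0.06 per day); exponential time to last dose, capped at Day 28, with median 10 days on placebo and 8, 7 or 5 on active; a *tail* of 0, 5 or 7 days counted after the last dose. Several tails are used because the residual effect period is not visible.

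**Formula.** With S(t) = exp(−t·ln 2 / median), the chance that the last dose is on Day t is p(t) = S(t−1) − S(t) for t < 28, and p(28) = S(27). The crude proportion with an event is the sum over t of p(t)·[1 − exp(−h(t + tail))].

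**Equal hazards, h = 0.03, medians 10 and 7 days:**

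| Tail (days) | Placebo | Active | Difference (points) | Ratio | Patients of 65 |
|---|---|---|---|---|---|
| 0 | 29.3% | 23.8% | −5.6 | 0.81 | 19.1 v 15.4 |
| 5 | 39.2% | 34.4% | −4.8 | 0.88 | 25.5 v 22.3 |
| 7 | 42.7% | 38.2% | −4.5 | 0.89 | 27.8 v 24.8 |

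(Differences are from unrounded proportions.) Over all the assumed values the difference runs from −1.4 to −14.5 points and the ratio from 0.61 to 0.95. The true hazard ratio is 1.00 throughout.

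**A true excess.** If the hazard on active is 25% higher (0.0375), with the same medians, the crude ratios are 0.96, 1.03 and 1.05 for tails of 0, 5 and 7 days. A common 28-day window would show 1 − exp(−0.03 × 28) = 56.8% against 1 − exp(−0.0375 × 28) = 65.0%, a ratio of 1.14. With an excess of 50% the crude ratios are 1.10, 1.17 and 1.18.

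**Sampling error.** The 95% half-width of a difference between two arms of 65 is 1.96·√(2p(1−p)/65). It is 13.8 points at p = 0.20, 16.4 at 0.35 and 17.2 at 0.50.

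**Do rates per patient-day solve it?** Only if the hazard is roughly constant. Assume a hazard of 0.08 per day for 5 days and 0.02 after that, the same in both arms, with windows of 16 and 14 days.
- Cumulative hazard: 0.40 + 11 × 0.02 = 0.62, and 0.40 + 9 × 0.02 = 0.58.
- Crude: 1 − exp(−0.62) = 46.2% and 1 − exp(−0.58) = 44.0%, ratio 0.95.
- Mean days to first event or end of window: (1 − e^−0.40)/0.08 + e^−0.40·(1 − e^−0.22)/0.02 = 10.74, and with 0.18 in place of 0.22, 9.64.
- Rates: 0.462/10.74 = 4.30 and 0.440/9.64 = 4.56 per 100 days, ratio 1.06.

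With equal hazards the rate now suggests harm in the arm with the shorter window. Rates alone therefore cannot carry the comparison.

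**The case against.** **A reader might infer that adverse-event collection stops at discharge.** It does not. The window follows the last dose: all events are collected to FUP 1, and related SAEs, related AESIs and cancers to Day 90.

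**A reader might infer that the plan makes a drug that speeds discharge look safer.** The documents do not settle the direction. Early death or early stopping also shortens the window, so a harmful drug can gain from it. A drug that keeps sicker patients alive and in hospital can look worse. Events clustered in the first days are little affected, and fewer events after faster recovery can be a real benefit.

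**A reader might infer that crude percentages are all that will be reported.** This cannot be confirmed. The sponsor guideline was not available, and part of Protocol 7.2.5 is redacted. Nor does the sentence on counting patients rule out person-time: it chooses patients over event counts, and a first-event rate complies with it.

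The other side can add that deaths, and the composite at Day 29, have fixed-day analyses; that tabulated exposure would show unequal durations; that safety is descriptive with no testing; and that the illustrated bias is mostly below sampling error.

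All of this stands, and it limits the point without removing it. Non-fatal SAEs have no fixed-day analysis outside that composite. Showing exposure does not adjust for it. Bias does not average out as sampling error does. An outcome-dependent window is a feature of this trial and should be handled in its own SAP, whatever a general guideline says.

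**Conclusion.** The point holds in this limited form. Time at risk for adverse events is tied to the last dose and so to recovery, death or early stopping. The visible SAP text specifies only the number and percentage of patients with events. The between-arm comparison of adverse events and non-fatal SAEs can therefore be biased, in either direction, when treatment duration differs by arm.

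The likely size is a few percentage points: about 5 in the central case, 1.4 to 14.5 over the assumed range. This rests on assumed constant and equal hazards, assumed stays and an assumed tail, none of which the documents give. It affects how descriptive tables are read, not a test, and it leaves the mortality analyses untouched. The change is worth making because it is cheap.

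**What to change.** 1. **Protocol 5.2.6.2.1:** collect all SAEs, regardless of relatedness, to Day 29 for every patient. Use the planned contacts, where the Flow Chart already lists adverse-event evaluation. FUP 3 is skipped within 2 days of EOT or FUP 1: with EOT on Day 23, FUP 1 is Day 27 and the next contact is Day 60. For such patients, ask about the interval to Day 29 at the next contact.
2. **SAP 7.8 and 7.8.1:** tabulate patients with an SAE by arm over the common Day 1–29 window, fatal SAEs included, as the main between-arm SAE comparison. State it as an exception to the on-treatment restriction.
3. **SAP 7.8.1:** beside the crude percentages, give first-event rates per 100 patient-days at risk (first dose to first event, end of the treatment-emergent window, death or last contact), or cumulative incidence with death as a competing event. Do this for any AE, SAEs, AEs leading to discontinuation and AESIs. State that rates assume a roughly constant hazard and can mislead if events cluster early, and that censoring at the end of the window assumes patients leaving it resemble those who remain.

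**Cost:** item 1 needs a protocol amendment and adds a few SAE forms. Items 2 and 3 add SAP wording and a few tables. Item 3 needs no new data, since dose dates and event onset dates are already recorded (Protocol 4.3, 8.3.1). The primary analysis and patient management do not change.

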**4. CHANGES IN THE PLANNED ANALYSIS OF THE STUDY**

This section is not applicable as no change has been made.

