**Table 6.1: 1 Definition of treatment periods**

Analysing Treatment Period	Start Date (including)	Stop Date (including)
Screening	Day of informed consent	Date of first administration of study medication -1 day (It could be the same day of informed consent)
On-treatment period	Day of first administration of study medication	
Post-treatment		Last contact date

For detailed rules for assigning AEs to these time periods, please refer to Section 7.8.1.

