**Table 6.3: 1 Patient sets analysed**

[figure not shown]
Class of endpoint	Patient set			
	Screened set	Full analysis set	Randomised set	Per Protocol Set
Efficacy analysis		X	si	02
Safety analysis		X		
Patients disposition	X			

 S = Sensitivity analyses

 0 : Optional

The FAS will be used for the efficacy analyses following the intention-to-treat (ITT) principle in assigning patients to treatment groups, i.e., efficacy analyses will be analysed as randomised using the FAS.

If a patient receives incorrect medication for the entire treatment period, efficacy will be analysed as randomized and safety will be analysed as treated. If a patient receives incorrect medication for part of the treatment period, such cases will be discussed in the RPM.

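### SAP 7.8.1 assigns every pre-dose adverse event to screening and omits the protocol's rule that those worsening on treatment are treatment-emergent

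*SAP*

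**What the plan says.** Protocol 7.2.5 gives two routes to a treatment-emergent AE. The first is occurrence between the start of treatment and the end of the residual effect period. The second is worsening of an earlier event: "Adverse events that start before first drug intake and deteriorate under treatment will also be considered as 'treatment-emergent".

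SAP 7.8.1 adopts the same concept by name: "The analysis of AEs will be based on the concept of treatment emergent AEs". It then explains the concept by time of occurrence alone. Events from first intake to an interval after last intake go to the treatment arm. For earlier events it says: "All AEs occurring before first drug intake will be assigned to 'screening".

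Three other SAP statements bear on this:

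- SAP 6.1, below its table of periods, makes 7.8.1 the governing text: "For detailed rules for assigning AEs to these time periods, please refer to Section 7.8.1".
- SAP 7.8 sets the scope: "All safety analyses will be performed on the FAS during on-treatment period".
- SAP 4, on changes to the planned analysis: "This section is not applicable as no change has been made".

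On the arm to which events are attributed, SAP 7.8.1 says that on-treatment events "will be assigned to the randomised treatment". For a patient given the wrong medication throughout, SAP 6.3 says that "efficacy will be analysed as randomized and safety will be analysed as treated".

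**The concern.** The protocol counts worsening of a pre-dose event while on study drug, and the SAP rule as worded does not. Such a worsening can be a sign of harm. The tables that SAP 7.8.1 plans for serious AEs, AEs leading to discontinuation, AEs of at least moderate severity and related AEs are where the two arms are compared on it.

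The situation can arise in this trial. Protocol 5.2.6.2.1 collects AEs from informed consent, and footnote c of the Flow Chart lets the screening visit fall up to 3 days before Visit 2. The patients are acutely ill inpatients on oxygen or non-invasive ventilation. A mild event noted during screening could become severe after dosing starts. The protocol would tabulate it as treatment-emergent; the SAP would leave it under screening.

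**Working it through.** This is a comparison of texts. The plan states no figure on this point, so there is none to reproduce.

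**1. Do the two rules differ?** Take an AE that starts after consent and before first intake, then worsens on drug within the same record.

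| Source | Test applied | Result |
|---|---|---|
| Protocol 7.2.5 | Started before first intake and deteriorated under treatment | Treatment-emergent |
| SAP 7.8.1 | Occurred before first intake | Screening |

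The results differ. The SAP rule begins with the word all and carries no exception.

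**2. Does another part of the SAP restore the protocol rule?** SAP 6.1 defers to 7.8.1 for the detailed assignment rules. SAP 3 says the plan is based on protocol Section 7, but 7.8.1 then writes out its own definition. SAP 4 lists no change. Nothing in the SAP repeats the worsening rule.

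**3. Is redaction the cause?** No. The gap in 7.8.1 concerns the interval after last intake. The pre-dose rule is complete, and the conflict lies between current texts.

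**4. What follows for the tables?** By SAP 7.8 the safety analyses cover the on-treatment period, so an event held under screening is not in those tables.

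**5. When does this happen?** Only when the worsening stays in the original record. Protocol 5.2.6.1.1 asks for worsening of the underlying disease or of another pre-existing condition to be recorded as an AE. If a site opens a new record dated at the worsening, that record falls in the on-treatment period under either rule. The protocol does not say whether an AE that began after consent gets a second record when it worsens.

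**6. How many patients?** The affected number over both arms is

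N × p × q × r

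where N = 130 is the planned number randomised (protocol synopsis), p is the share with an AE starting between consent and first dose, q is the share of those whose event worsens on treatment, and r is the share of those whose worsening stays in the original record. The documents give none of p, q or r, so the number cannot be derived.

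**7. What does one patient weigh?** With 65 per arm, 1/65 = 0.0154, or 1.5 percentage points of an arm's incidence in the category concerned. SAP 7.8.1 counts patients, not events. A patient with another on-treatment AE in the same category is already counted, and the incidence does not move.

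**The case against.** The strongest reply is that this is an omitted sentence, not a changed analysis. SAP 3 assumes familiarity with the protocol and builds on its Section 7, where the worsening rule stands. SAP 7.8.1 invokes the treatment-emergent concept, and SAP 4 says nothing was altered. The SAP also speaks of events occurring, not starting, before first intake. This shows that the departure may well be unintended. It does not remove it, because a programmer who follows 7.8.1 literally has a complete rule, and that rule gives a different result from the protocol's.

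Two mitigations stand as limits on the point. Worsening may be entered as a new AE (step 5 above). The sponsor's AE guideline, cited in 7.8.1 for further detail on summarising AEs, may also deal with worsening; its content is not in the documents. Neither is certain to apply, and an unqualified rule in the SAP should not depend on an outside text to reverse it.

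A reader might infer that deteriorating transaminases or renal function would go unseen. The documents do not support that. Both are scheduled safety laboratory tests (protocol 5.2.3), compared with reference ranges under protocol 7.2.5 and set against the last pre-treatment value under SAP 6.7. They would appear in the laboratory analyses whatever the AE flag. Reporting of individual serious AEs to the sponsor (protocol 5.2.6.2.2) is likewise unaffected.

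A reader might also infer from the randomised-treatment wording that events on active drug in a mis-dosed patient would be tabulated under placebo. SAP 6.3 has a specific as-treated rule for medication that is wrong throughout, and it sends partial cases to the report planning meeting. That rule governs the general sentence in 7.8.1, so only a cross-reference is missing.

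**Conclusion.** The point holds in a limited form. SAP 7.8.1 departs from protocol 7.2.5 on AEs that start before first dose and worsen on treatment, and SAP 4 does not declare it. Followed as written, and where the worsening is kept in the original record, such an event is left out of the on-treatment AE tables.

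A reader might want a count. Assuming, for illustration only, p of 5% to 15%, q of 20% to 40% and r = 1, the formula gives 130 × 0.05 × 0.20 = 1.3 to 130 × 0.15 × 0.40 = 7.8 patients over both arms. Those shares have no source in the documents, and r = 1 is the least favourable case, so the range is not a finding. The number is probably small: screening lasts at most 3 days and may fall on the same day as Visit 2, and protocol 3.3 asks sites to keep the time to treatment short.

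No efficacy endpoint is touched. The safety analyses are descriptive and the rule is the same in both blinded arms. The reason to act is that the conflict is plain in the text and cheap to remove.

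**What to change.** - In SAP 7.8.1, after the rule for pre-dose events, carry over the protocol's sentence with a reference to CTP 7.2.5. The protocol's own term for worsening is enough; further criteria, such as a seriousness test or a set date of worsening, would go beyond it.
- State how worsening of a screening-onset AE is recorded in the eCRF (same record or new record), and base the treatment-emergent flag on that.
- If the narrower SAP rule is intended, declare and justify it in SAP 4 instead.
- As a minor alignment, add a cross-reference to SAP 6.3 beside the mention of randomised treatment in 7.8.1.

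The cost is one sentence, a cross-reference and a small change to the flag's derivation. If worsening is kept in the original record, the flag also needs information in the data that the event deteriorated after first intake. If sites already enter worsening as a new AE, the added sentence changes no table.
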